#### 9.8.4 Duration of Overall Complete Response

The period measured from the time that measurement criteria are met for complete response until the first date that recurrent disease is objectively documented.

#### 9.8.5 Objective Response Rate

Objective response rate (ORR). ORR will be measured using two timepoints, per RECIST 1.1. “ORR1” will be assessed using baseline imaging in comparison to imaging obtained after completion of induction durvalumab and chemoradiation. “ORR2” will be assessed using imaging after completion of induction durvalumab and chemoradiation in comparison to imaging obtained after completion of consolidation durvalumab.

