### 2.2.2 Secondary Endpoints

- Objective response rate (ORR). ORR will be measured using two timepoints, per RECIST 1.1. “ORR1” will be assessed using baseline imaging in comparison to imaging obtained after completion of induction durvalumab and chemoradiation. “ORR2” will be assessed using imaging after completion of induction durvalumab and chemoradiation in comparison to imaging obtained while receiving, and after completion of, consolidation durvalumab.

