4: Vital signs to include temperature, pulse, respirations, blood pressure, weight, and height (screening only) and ECOG performance status. Patients will be monitored before, during and after the durvalumab infusion with assessment of vital signs. Patients are monitored (pulse rate, blood pressure) every 30 minutes (- 5 minutes/+ 10 minutes), during the infusion period (including times where infusion rate is slowed or temporarily stopped).

5: CBC with differential and platelet to include: WBC, ANC, Hgb, Hct, PLT. CMP to include sodium, potassium, chloride, creatinine, blood urea nitrogen; liver function tests (LFTs) to include AST, ALT, total bilirubin, alkaline phosphatase. Thyroid Function testing should be performed at

screening, at start of consolidation durvalumab, then every 3 cycles during consolidation durvalumab. TSH will be obtained. T4 and T3 including free versus total testing is at the discretion of the site investigator.

6: For women of childbearing potential (WOCBP): urine or serum  $\beta$ hCG will be done at screening and within 24 hrs of 1st dose of study drug. During treatment with consolidation durvalumab, a pregnancy test should be performed every 4 weeks. If a urine test is done and it is positive or cannot be confirmed as negative, a serum pregnancy test will be required.

7: Tumor assessments to be performed at (1) screening (PET scan may be within 42 days prior to C1D1) (2) within 0-24 days after completion of chemoradiation/prior to C1D1 of consolidation durvalumab, then every 3 months (about every 3 cycles/ $\pm$  7 business days) during consolidation durvalumab. Screening tumor assessment will consist of evaluation by CT scans of chest (contrast enhanced), PET scan, and contrast-enhanced MRI or CT of the brain. Response assessment imaging will include CT scans of chest, abdomen, and pelvis (contrast enhanced). MRI or CT brain or PET scan after screening should be performed as clinically indicated. Imaging selected for each subject should remain the same throughout the study. Tumor imaging at treatment discontinuation/D30 safety follow up visit is at discretion of site investigator. If tumor assessments are available for subjects who have not yet experienced progressive disease (PD) at the time treatment is discontinued, the follow-up tumor evaluations will be documented in the eCRF until PD or death is confirmed, or until another treatment is initiated. A window of 7 days may be applied to obtain scans.

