12: After the D100 safety visit, subjects who discontinue treatment for any reason without documented disease progression will be followed for disease progression every 3 months up to 12 months after initiation of consolidation durvalumab. Once disease progression is documented, subjects will enter a survival follow up period every 6 months for 1 year from the time of documented progression or until 1 year after initiation of consolidation durvalumab. Follow up may be accomplished via clinic visit, phone call, or other avenues as appropriate. A window of  $\pm$  14 days will be applied to follow up.

13: If screening (baseline) CBC and CMP were performed within 7 days of Day 1 of treatment, these do not need to be repeated. All laboratory assessments should be done prior to treatment.

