##### 12.2.2 Definition of Secondary Endpoints

1. Objective response rate (ORR). ORR will be measured using two timepoints, using RECIST 1.1. "ORR1" will be assessed after completion of induction and chemoradiation

in comparison with baseline imaging. “ORR2” will also be assessed comparing first imaging after completion of induction and chemoradiation to imaging after consolidation durvalumab.

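### ORR2 is defined on two different sets of scans, and the post-consolidation scan that the narrower set relies on is not clearly guaranteed

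*Combined protocol and SAP*

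**What the plan says.** Three sections define ORR2. All start from the scan after induction and chemoradiation, and all invoke RECIST 1.1. They differ in what that scan is compared with.

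- Section 2.2.2 (Secondary Endpoints): "in comparison to imaging obtained while receiving, and after completion of, consolidation durvalumab".
- Section 9.8.5 (Objective Response Rate): "in comparison to imaging obtained after completion of consolidation durvalumab".
- Section 12.2.2 (Definition of Secondary Endpoints): "comparing first imaging after completion of induction and chemoradiation to imaging after consolidation durvalumab".

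The ORR analysis plan in 12.6.2 names tests for comparing two time points. It does not say which scans enter ORR2, who is in the denominator, or what happens to a patient without the required scan. Section 9.8.2 requires a response to be confirmed at least four weeks after it is first met.

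The imaging schedule is in Section 7. Footnote 7 calls for scans every 3 months, about every 3 cycles, during consolidation. It then says: "Tumor imaging at treatment discontinuation/D30 safety follow up visit is at discretion of site investigator". Later scans are recorded under a condition: "If tumor assessments are available for subjects who have not yet experienced progressive disease (PD) at the time treatment is discontinued". Under footnote 12, patients who stop without progression enter follow-up after the day 100 visit and "will be followed for disease progression every 3 months up to 12 months after initiation of consolidation durvalumab". The footnote adds: "Follow up may be accomplished via clinic visit, phone call, or other avenues as appropriate".

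**The concern.** ORR is the only secondary objective (2.1.2), and 13.3 requires results of secondary objectives to be posted. With two scan sets in force, the same data can give two ORR2 rates, and the choice between them could be made after the data are seen.

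The narrower set raises a second problem. It discards the on-treatment scans that the protocol does schedule and relies on a scan that the protocol does not firmly require. If having that scan is related to how the patient is doing, the rate among patients who have it may not represent all those treated.

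**Working it through.** The plan attaches no figure to ORR2 (no expected rate, target, hypothesis or sample size), so there is nothing to reproduce. The check compares the definitions with the imaging dates.

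**Inputs.** Consolidation is up to 12 cycles of 28 days (5, 5.3, 7). Scans are about every 3 cycles (footnote 7). Safety visits are 30 and 100 days after the last dose, each ± 7 days (footnote 11). Progression follow-up ends 12 months after consolidation starts (footnote 12). Assumptions: consolidation C1D1 is day 1, and there are no delays.

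**Dates for a patient who completes 12 cycles.**
- Last dose: 1 + 11 × 28 = day 309. Cycle 12 ends on day 309 + 27 = 336.
- Scans every 3 cycles: 1 + 84k for k = 1 to 4, giving days 85, 169, 253 and 337.
- Day 30 visit: 309 + 30 = day 339, window 332 to 346.
- Day 100 visit: 309 + 100 = day 409, window 402 to 416.
- 12-month limit: 1 + 365 = day 366.

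The first three scans are on treatment. The fourth, on day 337, is 28 days after the last dose and inside the day 30 window, where imaging is optional. If the interval is read as calendar months instead, the scans fall at about days 92, 184, 275 and 366, and the fourth lands on the follow-up limit. Day 100 falls after that limit (409 > 366), so long-term follow-up adds no scheduled scan for completers.

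**Dates for early stoppers.** After c cycles the last dose is on day 1 + 28(c − 1). Assume that the first 3-monthly visit is 91 days after day 100.
- 7 cycles: 169 + 100 + 91 = day 360, before day 366.
- 8 cycles: 197 + 100 + 91 = day 388, after it.

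So only patients who stop after 7 or fewer cycles reach a long-term follow-up visit before the limit, and footnote 12 lets that contact be by telephone.

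**One patient under each definition.** Take a partial response on day 85, confirmed on day 169 (84 days later, so 9.8.2 is met), then progression on day 253.
- Under 2.2.2, read as best response: responder.
- Under 9.8.5 and 12.2.2: not a responder, because no scan after consolidation shows a response.

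**Confirmation.** Under the narrower set, a response first seen on a single post-treatment scan cannot be confirmed by that scan, so 9.8.2 needs a second one at least four weeks later.

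**The case against.** The strongest reply has four parts.

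1. Section 2.2.2 lists scans and never says best response. This stands. None of the three sections states how several scans are combined, although 9.7 is headed as an evaluation of best overall response. The patient example is therefore conditional on that reading.

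2. The after-only scans are a subset of those in 2.2.2. A reader might infer that the definitions exclude each other. They do not: they are two different quantities that can give different rates and need to be harmonised.

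3. The post-treatment scan may exist in practice. The calendar marks CT in the safety and long-term follow-up columns, and the scan near day 337 could be read as the last scheduled consolidation scan. This stands in part. Those marks point back to footnote 7, which carries the discretion, and the documents do not say which rule governs near day 337. A reader might infer that the scan is missing by design according to outcome. No section says so. That availability follows the patient's course is a plausible inference only.

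4. The stakes are limited: ORR is to be estimated, with no target rate or go/no-go role. This is correct, and it bounds the importance of the point.

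**Conclusion.** The point holds as an inconsistency in the scan window of the only secondary endpoint. Section 2.2.2 conflicts with 9.8.5 and 12.2.2, and no section resolves it. Under the latter two, the necessary scan is not clearly guaranteed, particularly for patients who complete 12 cycles. The date count assumes no delays, and for early stoppers a first long-term follow-up visit 91 days after day 100.

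The size of the effect cannot be computed from the documents. A reader might be tempted to take the 28.4% response rate quoted in Section 1.1 for the historical durvalumab arm and reduce it by an assumed loss. The documents do not support this. That rate is not an expectation for ORR2, no loss rate is given, and such a figure would mix relapse with missing scans. Even the direction depends on an unstated rule: patients without a scan lower the rate if kept as non-responders, but dropping them could raise it.

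The primary endpoint and its sample size are not affected. This should be corrected before analysis.

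**What to change.** Use one ORR2 definition, in the same words, in 2.2.2, 9.8.5 and 12.2.2, and refer to it in 12.6.2. Which scan set to adopt is the sponsor's decision, but that of 2.2.2 is preferable because it uses scans already scheduled. The definition should state:

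- **Measure:** best RECIST 1.1 response relative to the post-chemoradiation scan.
- **Scans:** all from consolidation C1D1 to progression, new therapy or end of follow-up.
- **Confirmation:** as in 9.8.2.
- **Denominator:** all patients who start consolidation, with those who have no later scan counted as non-responders. Section 12.5 defines evaluability only for PFS, so ORR2 needs its own statement.

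If the after-only definition is kept instead, footnote 7 must be aligned with it, and the plan must say what completion means for a patient who stops early.

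The cost of the preferred change is minor wording and a possibly lower stated rate, because patients without a later scan stay in the denominator. No new scans are needed.

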#### 9.8.7 Time to Progression

A measurement from the date of Cycle 1 Day 1 of induction durvalumab until the criteria for disease progression is met as defined by RECIST 1.1. Subjects who have not progressed or have died due to any cause will be right-censored at the date of the last disease evaluation or date of death.

#### 9.8.8 Progression Free Survival

12-month progression-free survival will be measured using imaging prior to C1D1 consolidation durvalumab (between 1-42 days after completion of chemoradiation) as baseline. This timepoint is selected in order to compare with the PACIFIC trial 12-month progression-free survival as historical control. 12-month PFS will be defined as the time from the date of CT prior to beginning consolidation radiation until the date of objective disease progression or death (by any cause in the absence of progression), as measured for the 12-month period after initiation of consolidation durvalumab.

### 10 DRUG INFORMATION

#### 10.1 Durvalumab

Please refer to Investigator’s Brochure for detailed information regarding this medication.

Durvalumab is a human monoclonal antibody (mAb) of the immunoglobulin G1 kappa (IgG1κ) subclass that inhibits binding of programmed cell death ligand 1 (PD-L1)(B7 homolog 1

[B7H1], cluster of differentiation [CD]274) to programmed cell death 1 (PD-CD279) and CD80 (B71). Durvalumab is composed of 2 identical heavy chains and 2 identical light chains, with an overall molecular weight of approximately 149 kDa. Durvalumab contains a triple mutation in the constant domain of the immunoglobulin (Ig) G1 heavy chain that reduces binding to complement protein C1q and the fragment crystallizable gamma (Fc $\gamma$ ) receptors involved in triggering effector function.

#### 10.1.1 Supplier/How Supplied

The Investigational Products Supply section of AstraZeneca/MedImmune will supply durvalumab to the investigator as a solution for infusion after dilution. Durvalumab is manufactured by AstraZeneca/MedImmune. AstraZeneca/MedImmune will supply durvalumab at no charge to subjects participating in this clinical trial.

Durvalumab will be supplied as a 500 mg vial solution for infusion after dilution. The solution contains 50 mg/mL durvalumab, 26 mM histidine/histidine hydrochloride, 275 mM trehalose dihydrate, and 0.02% (weight/volume) polysorbate 80; it has a pH of 6.0 and density of 1.054 g/mL. The nominal fill volume is 10.0 mL. Durvalumab must be used within the individually assigned expiry date on the label.

The site investigator shall take responsibility for and shall take all steps to maintain appropriate records and ensure appropriate supply, storage, handling, distribution, and usage of investigational product in accordance with the protocol and any applicable laws and regulations.

#### 10.1.2 Preparation and Administration

The dose of durvalumab for administration must be prepared by the Investigator's or site's designated IP manager using aseptic technique. Total time from needle puncture of the durvalumab vial to the start of administration should not exceed:

- 24 hours at 2°C to 8°C (36°F to 46°F)
- 4 hours at room temperature

A dose of 1500 mg (for patients >30kg in weight) will be administered using an IV bag containing 0.9% (w/v) saline or 5% (w/v) dextrose, with a final durvalumab concentration ranging from 1 to 15 mg/mL, and delivered through an IV administration set with a 0.2- or 0.22 $\mu$ m filter. Add 30.0 mL of durvalumab (i.e., 1500 mg of durvalumab) to the IV bag. The IV bag size should be selected such that the final concentration is within 1 to 15 mg/mL. Mix the bag by gently inverting to ensure homogeneity of the dose in the bag.

Standard infusion time is one hour, however if there are interruptions during infusion, the total allowed infusion time should not exceed 8 hours at room temperature.

The IV line will be flushed with a volume of IV diluent equal to the priming volume of the infusion set used after the contents of the IV bag are fully administered, or complete the infusion according to institutional policy to ensure the full dose is administered.

If either preparation time or infusion time exceeds the time limits a new dose must be prepared from new vials. Durvalumab does not contain preservatives, and any unused portion must be discarded.

If in-use storage time exceeds these limits, a new dose must be prepared from new vials. Infusion solutions must be allowed to equilibrate to room temperature prior to commencement of administration.

No incompatibilities between durvalumab and polyvinylchloride or polyolefin IV bags have been observed. A durvalumab dose of 1500 mg will be administered using an IV bag containing 0.9% (w/v) saline or 5% (w/v) dextrose, with a final durvalumab concentration ranging from 1 to 15 mg/mL, and delivered through an IV administration set with a 0.2- or 0.22- $\mu$ m filter.

Add 30.0 mL of durvalumab to the IV bag. The IV bag size should be selected such that final concentration is within 1 to 15 mg/mL. Mix the bag by gently inverting to ensure homogeneity of the dose in the bag.

Durvalumab will be administered at room temperature (approximately 25°C) by controlled infusion into a peripheral or central vein. Following preparation of durvalumab, the entire contents of the IV bag should be administered as an IV infusion over approximately 60 minutes (- 5 minutes/+ 10 minutes), using a 0.2- or 0.22- $\mu$ m filter. Less than 55 minutes is considered a deviation.

Do not co-administer other drugs through the same infusion line.

The IV line will be flushed with a volume of IV solution (0.9% [w/v] sodium chloride injection equal to the priming volume of the infusion set used after the contents of the IV bag are fully administered, or complete the infusion according to institutional policy to ensure the full dose is administered

Standard infusion time is 1 hour. However, if there are interruptions during infusion, the total allowed time should not exceed 8 hours at room temperature. The table below summarizes time allowances and temperatures.

In the event that either preparation time or infusion time exceeds the time limits outlined in the table, a new dose must be prepared from new vials. Durvalumab does not contain preservatives, and any unused portion must be discarded.

#### 10.1.3 Storage and Stability

Investigational product vials are stored at 2°C to 8°C (36°F to 46°F) and must not be frozen. Drug product should be kept in original packaging until use to prevent prolonged light exposure.

Unopened vials of Durvalumab liquid Drug Product must be stored at 2°C to 8°C (36°F to 46°F). Protect from light.

#### 10.1.4 Adverse Events

For information on all identified and potential risks with durvalumab refer to the current version of the durvalumab IB.

The majority of treatment-related AEs were manageable with dose delays, symptomatic treatment, and in the case of events suspected to have an immune basis, the use of established treatment guidelines for immune-mediated adverse events.

Immunotherapy adverse related reactions: Individuals receiving Durvalumab therapy are at increased risk for immune related adverse events such as pneumonitis/interstitial lung disease, hepatitis/increases in transaminases, colitis and intestinal perforation, development of type I diabetes mellitus, thyroid dysfunction, adrenal insufficiency, hypophysitis/hypopituitarism. Other effects include an immunotherapy-induced rash, immune thrombocytopenia, nephritis, pancreatitis/increases in amylase and lipase, and myocarditis. Severe infections can also occur in those receiving Durvalumab therapy. Infusion related reactions: Severe infusion related reactions have occurred and those with Grade III or IV reactions should have Durvalumab discontinued permanently. Other side effects: Fatigue, peripheral edema, pyrexia, decreased appetite, diarrhea, constipation, nausea/vomiting, cough, and dyspnea have also been reported.

#### 10.2 Chemotherapy

Please refer to the current package insert for complete prescribing and toxicity information for each chemotherapy medication. Institutional guidelines may be used for preparation and administration of chemotherapy used. The chemotherapy utilized will be sourced commercially.

### 11. ADVERSE EVENTS

The descriptions and grading scales found in the NCI CTCAE v5 will be utilized for AE assessment. A copy of the CTCAE v5 can be downloaded from the CTEP website at <http://ctep.cancer.gov>. All forms for AE/SAE recording and reporting can be found in the EDC system (Documents and Information Tab).

#### 11.1 Definitions

##### 11.1.1 Adverse Event (AE)

An AE is any untoward medical occurrence whether or not considered related to the study drug that appears to change in intensity during the course of the study. The following are examples of AEs:

- Unintended or unfavorable sign or symptom
- A disease temporally associated with participation in the protocol
- An intercurrent illness or injury that impairs the well-being of the subject

Hospitalization for elective surgery or routine clinical procedures that are not the result of an AE (e.g., surgical insertion of central line) should not be recorded as an AE.

Disease progression should not be recorded as an AE, unless it is attributable to the study regimen by the site investigator.

#### 11.1.2 Serious Adverse Event (SAE) A

SAE is an adverse event that:

- Results in death.
- Development of a new cancer. New primary cancers are those that are not the primary reason for the administration of the IP and have been identified after the patient's inclusion in this study.
- Is life-threatening (defined as an event in which the subject was at risk of death at the time of the event; it does not refer to an event which hypothetically might have caused death if it were more severe)
- Requires inpatient hospitalization for >24 hours or prolongation of existing hospitalization. NOTE: Hospitalization for anticipated or protocol specified procedures such as administration of chemotherapy, central line insertion, metastasis interventional therapy, resection of primary tumor, or elective surgery, will not be considered serious adverse events.
- Results in persistent or significant disability/incapacity
- Is a congenital anomaly or birth defect
- Is an important medical event (defined as a medical event(s) that may not be immediately life-threatening or result in death or hospitalization but, based upon appropriate medical and scientific judgment, may jeopardize the subject or may require intervention (e.g., medical, surgical) to prevent one of the other serious outcomes listed in the definition above). Examples of such events include, but are not limited to, intensive treatment in an emergency room or at home for allergic bronchospasm; blood dyscrasias or convulsions not resulting in hospitalization; or the development of drug dependency or drug abuse.

#### 11.1.3 Unexpected Adverse Event

For this study, an AE is considered unexpected when it varies in nature, intensity or frequency from information provided in the current IB, prescribing information or when it is not included in the informed consent document as a potential risk. Unexpected also refers to AEs that are mentioned in the IB as occurring with a class of drugs or are anticipated from the pharmacological properties of the drug, but are not specifically mentioned as occurring with the particular drug under investigation.

